5.1.1.1 Common Adverse Events

According to the package insert, ³ adverse reactions experienced by at least 4% of subjects on AUSTEDO and with a greater incidence than on placebo include somnolence, diarrhea, dry mouth, fatigue, urinary tract infection, insomnia, anxiety, constipation and contusion.

5.1.1.2 Serious Adverse Events

A serious adverse event (SAE) is any AE occurring at any dose that:

- results in death
- is life-threatening (subject is at immediate risk of death at the time of the event)
- requires inpatient hospitalization or results in prolongation of existing hospitalization
- results in persistent or significant disability/incapacity
- is a congenital anomaly/birth defect in the offspring of a subject who received study drug
- is a significant or important medical event, i.e., an event that, based upon appropriate medical judgment, may jeopardize the subject and may require medical or surgical intervention to prevent one of the above mentioned criteria (examples of such events are intensive treatment in an emergency room or at home for allergic bronchospasm, blood dyscrasias or convulsions that do not result in hospitalization, or development of drug dependency or drug abuse).

When a causality assessment is provided for an SAE, a rationale for the assessment will be included, so that a better understanding of the reported event can be compiled. The rationale will be accompanied by all available supporting evidence, including relevant laboratory tests, histopathology evaluations, and

the results of other diagnostic procedures. The Investigator's rationale with supporting evidence is valuable when the Sponsor performs a cumulative analysis of similar events.

A Suspected Unexpected Serious Adverse Reaction (SUSAR) is any serious adverse event that is considered related to the investigational product, and that is also unexpected. SUSARs qualify for expedited reporting to applicable Health Authorities and IRB/REB/IECs.

According to the package insert,³ the following serious adverse reactions can happen with the use of AUSTEDO:

- Depression and suicidality: Subjects with Huntington's disease are at increased risk for depression, and suicidal ideation or behaviors (suicidality). AUSTEDO may increase the risk for suicidality in subjects with Huntington's disease. In a 12-week, double-blind, placebo-controlled trial, suicidal ideation was reported by 2% of subjects treated with AUSTEDO, compared to no subjects on placebo; no suicide attempts and no completed suicides were reported. Depression was reported by 4% of subjects treated with AUSTEDO.
- Neuroleptic malignant syndrome: A potentially fatal symptom complex sometimes referred to as Neuroleptic Malignant Syndrome (NMS) has been reported in association with drugs that reduce dopaminergic transmission. While NMS has not been observed in subjects receiving AUSTEDO, it has been observed in subjects receiving tetrabenazine (a closely related VMAT2 inhibitor). The management of NMS will include (1) immediate discontinuation of AUSTEDO; (2) intensive symptomatic treatment and medical monitoring; and (3) treatment of any concomitant serious medical problems for which specific treatments are available. Recurrence of NMS has been reported with resumption of drug therapy, and, thus, any subject developing this will be immediately withdrawn from the trial.
- Akathisia, agitation and restlessness: AUSTEDO may increase the risk of akathisia, agitation, and
 restlessness in subjects with Huntington's disease. In a 12-week, double-blind, placebocontrolled trial, akathisia, agitation, or restlessness was reported by 4% of subjects treated with
 AUSTEDO, compared to 2% of subjects on placebo. If a patient develops akathisia during
 treatment with AUSTEDO, the AUSTEDO dose will be reduced; some subjects may require
 discontinuation of therapy and withdrawal from the trial.
- Parkinsonism: AUSTEDO may cause parkinsonism in subjects with Huntington's disease. Druginduced parkinsonism has the potential to cause more functional disability than untreated chorea for some subjects with Huntington's disease. If a patient develops parkinsonism during treatment with AUSTEDO, the AUSTEDO dose will be reduced; some subjects may require discontinuation of therapy.
- Sedation and somnolence: Sedation is a common dose-limiting adverse reaction of AUSTEDO. In a 12-week, double-blind, placebo-controlled trial, 11% of AUSTEDO-treated subjects reported somnolence compared with 4% of subjects on placebo and 9% of AUSTEDO-treated subjects reported fatigue compared with 4% of placebo-treated subjects.
- QTc prolongation: Tetrabenazine increases the QTc by about 8 msec. A clinically relevant QT prolongation may occur in subjects treated with AUSTEDO who are co-administered a strong CYP2D6 inhibitor, which is why these subjects will not be allowed to titrate to more than 36 mg/day.
- Hyperprolactinemia: Tetrabenazine elevates serum prolactin concentrations, but it is unclear whether AUSTEDO has this effect. Caution is advised with the use of AUSTEDO in subjects with

known or suspected hyperprolactinemia, or in subjects with breast cancer with prolactin receptors.

- Binding to Melanin-Containing tissues: Possible accumulation of AUSTEDO in these tissues over time could cause long-term ophthalmologic effects.
- 5.1.2 Adverse Event Assessment Definitions

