1.3.1 Selection of AUSTEDO Dose and Schedule of Administration

AUSTEDO is available in 6, 9 and 12 mg tablets. To allow a precise dose titration among study subjects, only 6 mg tablets will be used in the AUDYT trial. As this is an open label trial, all subjects will receive the study drug; there is no placebo arm. All subjects will be instructed to take AUSTEDO with food, and not to chew, crush or break the tablets. The trial will consist of 3 periods:

1. Ramp-up period: During this titration period, AUSTEDO will be started at 12 mg/day and increased up to 48 mg/day for most study subjects, up to 36 mg/day for study subjects receiving a strong CYP2D6 inhibitor, or up to the maximum, well-tolerated dose for those subjects unable to tolerate the maximum recommended dose of AUSTEDO. Dose-limiting toxicity will be defined in this protocol as the development of any of the following during the titration period: a) new or worsening depression, b) worsening of dystonic symptoms, c) QTc increase of >39 but <60 milliseconds from baseline, or d) any other sign or symptom that, at the PI's discretion, would preclude further safe titration of the study drug. AUSTEDO will be increased by 6 mg/week as recommended in the package insert,³ as shown in Table 2 below:

Table 2
Recommended AUSTEDO titration

	Total daily dose (mg)
Week 1	12
Week 2	18
Week 3	24
Week 4	30
Week 5	36
Week 6	42
Week 7	48

- 2. Maintenance period: Once on the maximum dose, subjects will complete 6 weeks of treatment on that dose, unless a side effects ensues. If so, it will remain at the investigator's discretion whether to discontinue the study drug, or to reduce the dose to a new, maximum, well-tolerated dose, on which the study subject will complete 6 weeks of treatment. Details on dose reduction will be discussed further elsewhere in this protocol.
- 3. Post treatment period: Following 6 weeks of treatment with AUSTEDO, the medication will be discontinued and a final safety evaluation will be performed once the subject has been 1 week off study drug.
- 2. TRIAL OBJECTIVES
- 2.1 Primary Objective

To explore the safety and tolerability of the daily oral administration of AUSTEDO in adult study subjects with dystonia.

- 2.2 Secondary Objectives
 - 1. To establish the degree of symptomatic effect of AUSTEDO as measured by the Clinical Global Impression of Improvement Scale (CGI-I) after 6 weeks of AUSTEDO 48 mg daily, or at the highest tolerated dose.

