- Somnolence is a possible side effect of AUSTEDO use. The Stanford Sleepiness Scale (SSS) will be administered during all scheduled study Visits, including the early termination Visit, if such a Visit happens. Should this side effect develop, the investigator will decided whether to continue AUSTEDO at the current dose, to discontinue the study drug, or to reduce the dose to a new, maximum, well-tolerated dose.
- To assess the impact AUSTEDO may have on cognitive function, if any, the Mini Mental State Examination (MMSE) will be administered during Visits 1, 4 and during the early termination Visit, if such a Visit happens. It will remain at the investigator's discretion to either discontinue the study drug, or to reduce the dose to a new, maximum, well-tolerated dose if clinically-

- significant, new-onset cognitive impairment is identified at any point during the course of the trial, even if detected during Visits during which the MMSE is not administered.
- To screen for the development of drug-induced parkinsonism, a possible side effect of AUSTEDO use, the MDS-UPDRS (Part III) will be administered during Visits 1, 4 and during the early termination Visit, if such a Visit happens. It will remain at the investigator's discretion to either discontinue the study drug, or to reduce the dose to a new, maximum, well-tolerated dose if clinically-significant, new-onset drug-induced parkinsonism is identified at any point during the course of the trial, even if detected during Visits during which the MDS-UPDRS (Part III) is not administered.

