3.6.1.8 MDS-UPDRS (Part III)

To screen for the development of drug-induced parkinsonism, a possible side effect of AUSTEDO use, the MDS-UPDRS (Part III)²⁰ will be administered during Visits 1, 4 and during the early termination Visit, if such a Visit happens. It will remain at the investigator's discretion to either discontinue the study drug, or to reduce the dose to a new, maximum, well-tolerated dose if clinically-significant, new-onset drug-induced parkinsonism is identified at any point during the course of the trial, even if detected during Visits during which the MDS-UPDRS (Part III) is not administered. Figure 7 shown below shows this Scale embedded in a data capture form:

Figure 7

Date: DD – MMM – YYYYY Study subject number: ____

Visit Number (circle one): 1 4 Early termination Visit

The AUDYT Trial MDS-UPDRS (Part III)

3.1	Speech	
3.2	Facial expression	
3.3a	Rigidity- Neck	
3.3b	Rigidity- RUE	
3.3c	Rigidity- LUE	
3.3d	Rigidity- RLE	
3.3e	Rigidity- LLE	
3.4a	Finger tapping- Right hand	
3.4b	Finger tapping- Left hand	
3.5a	Hand movements- Right hand	
3.5b	Hand movements- Left hand	
3.6a	Pronation- supination movements- Right hand	
3.6b	Pronation- supination movements- Left hand	
3.7a	Toe tapping-Right foot	
3.7b	Toe tapping- Left foot	
3.8a	Leg agility- Right leg	
3.8b	Leg agility- Left leg	

3.9	Arising from chair			
3.10	Gait			
3.11	Freezing of gait			
3.12	Postural stability			
3.13	Posture			
3.14	Global spontaneity of movement			
3.15a	Postural tremor- Right hand			
3.15b	Postural tremor– Left hand			
3.16a	Kinetic tremor– Right hand			
3.16b	Kinetic tremor- Left hand			
3.17a	Rest tremor amplitude- RUE			
3.17b	Rest tremor amplitude- LUE			
3.17c	Rest tremor amplitude- RLE			
3.17d	Rest tremor amplitude- LLE			
3.17e	Rest tremor amplitude- Lip/jaw			
3.18	Constancy of rest			
	Were dyskinesias presen	□ No □ Yes		
	Did these movements interfere with ratings?	□ No □ Yes		

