LOWER FACE (including platysma)					
JAW & TONGUE					
LARYNX (including pharynx)					
NECK					
SHOULDER & PROXIMAL ARM		R	L		
ELBOW, DISTAL ARM, HAND		R	L		
PELVIS & UPPER LEG		R	L		
DISTAL LEG & FOOT		R	L		
TRUNK					
TOTAL SCORE (Sum of all body parts)					

Rate the patient according to body part indicated from 1-10, in relationship to all patients. A score of 0 is no dystonia in that body area. A score of 5 is moderate dystonia. A score of 10 is the most severe dystonia encountered. If the dystonia changes during the examination, rate the maximal dystonia. For mixed motor syndromes, rate only dystonia and not the other components.

- 3.7 Study Endpoints
- 3.7.1 Safety Endpoints
- 3.7.1.1 Primary Safety Endpoint

The primary safety endpoint for the AUDYT trial will be the proportion of study subjects able to titrate up to 48 mg/d (or up to 36 mg/d if receiving a strong CYP2D6 inhibitor) and able to complete the study at this dosage. The reason(s) why subjects are unable to titrate or maintain the maximal recommended AUSTEDO dose will be recorded and reported, when appropriate.

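### Section 5.1.1.2 requires a dose reduction for parkinsonism of any severity, while 2.3 and 3.6.1.8 provide for action only when it is clinically significant, so a non-significant case can count either way on the primary endpoint

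*Combined protocol and SAP*

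**What the plan says.** Three parts of the combined protocol and SAP bear on what happens when a subject develops parkinsonism.

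- **Section 5.1.1.2** (Serious Adverse Events) lists reactions taken from the package insert, opening with "the following serious adverse reactions can happen with the use of AUSTEDO". Its parkinsonism entry says: "If a patient develops parkinsonism during treatment with AUSTEDO, the AUSTEDO dose will be reduced", and adds that some subjects may need to stop. It sets no severity threshold and leaves no choice about whether to reduce.
- **Sections 2.3 and 3.6.1.8** (the MDS-UPDRS Part III entries) say: "It will remain at the investigator's discretion to either discontinue the study drug, or to reduce the dose to a new, maximum, well-tolerated dose". The condition for this is that "clinically-significant, new-onset drug-induced parkinsonism is identified at any point during the course of the trial".
- **The dose-limiting toxicity definition** (sections 1.3.1, 3.1 and 3.5.2.4) applies during titration. It names depression, worsening dystonia and a QTc increase, but not parkinsonism, which can enter only through item d: "any other sign or symptom that, at the PI's discretion, would preclude further safe titration of the study drug".

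The primary safety endpoint in section 3.7.1.1 is the proportion of subjects who reach 48 mg/day (36 mg/day with a strong CYP2D6 inhibitor) and are "able to complete the study at this dosage". Under sections 3.5.1.2 and 4.4.2, a reduction during ramp-up starts maintenance at the lower dose, and a reduction during maintenance holds until the end of the trial.

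**The concern.** The primary endpoint is a dosing outcome, so any rule that forces a reduction also decides who counts as a success. For parkinsonism judged not clinically significant, one section requires a reduction and two others trigger nothing. The headline proportion, and the tolerated dose reported for that subject, could then depend on which section the clinician followed rather than on how the drug was tolerated. It would also be unclear whether leaving the dose unchanged is a protocol deviation under section 6.2.

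Section 1.3 names parkinsonism among the effects that limit tetrabenazine and motivate this study. It is therefore an event for which the tolerability result most needs a single rule.

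**Working it through.** No stated figure has to be reproduced: the 15 subjects are a recruitment choice (section 3.3), with no alpha, power or effect size. The check compares the texts and then works out what one subject is worth.

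**Step 1. Follow one subject through each rule.** Take a subject who has reached the target dose and develops parkinsonism before the end of maintenance.

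| Parkinsonism judged | Under 5.1.1.2 | Under 2.3 and 3.6.1.8 |
|---|---|---|
| Clinically significant | Reduced, or stopped in some cases: failure | Reduced or stopped: failure |
| Not clinically significant | Reduced: failure | No action triggered: success if the dose is left unchanged and the subject completes |

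The sections agree in the first row and part in the second. The same split arises in ramp-up: a mandatory reduction fixes the subject below target, whereas under 2.3, 3.6.1.8 and item d titration may continue.

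**Step 2. Confirm that non-significant cases are foreseen.** Section 5.1.2.1 grades every adverse event and includes a mild category, so the second row is not empty by construction.

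**Step 3. Value of one subject.** With a denominator of 15 (assuming all 15 are enrolled and dosed), each subject classified differently moves the proportion by 1/15 = 6.7 percentage points. As an illustration with exact (Clopper-Pearson) 95% intervals:

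- 12/15 = 80.0% (51.9% to 95.7%)
- 11/15 = 73.3% (44.9% to 92.2%)

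**Step 4. Chance that the case arises at all.** The documents give no rate of non-significant parkinsonism in dystonia, so the rate p is an assumption. The chance of at least one affected subject among 15 is 1 − (1 − p)^15:

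- p = 2%: 1 − 0.98^15 = 26%
- p = 5%: 1 − 0.95^15 = 54%
- p = 10%: 1 − 0.90^15 = 79%

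**Step 5. When it would be noticed.** MDS-UPDRS Part III is scheduled at Visits 1 and 4 and at early termination. The complete physical and neurologic examination is at Visits 1 and 5 and at early termination. Visits 2 and 3 rely on adverse event review, and the weekly ramp-up contacts are by telephone. Sections 2.3 and 3.6.1.8 do cover parkinsonism noticed at visits without the scale, so earlier detection is possible. A case first found at Visit 4, in the last week of maintenance, leaves little dosing time for either rule to affect.

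**The case against.** The strongest reply is that 5.1.1.2 is background. The list is introduced as serious reactions from the package insert, and its parkinsonism entry speaks of Huntington's disease and functional disability. A reader could reasonably take 2.3 and 3.6.1.8 as the trial's procedure. This weakens the point without removing it. The same list carries instructions for this trial: a subject with neuroleptic malignant syndrome is withdrawn, and subjects on strong CYP2D6 inhibitors may not go above 36 mg/day. Nothing tells the reader which of its statements bind, and the parkinsonism sentence is not limited to serious cases.

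Three stronger readings are tempting, and the documents do not support them.

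- *That the sections give opposite orders for mild parkinsonism.* Sections 2.3 and 3.6.1.8 are silent on it; they do not say to hold the dose. Where section 2.3 means to offer an unchanged dose, as for somnolence, it says so. The discretion it gives for parkinsonism is between reducing and stopping. Section 3.5.1.2 also permits reductions at the investigator's discretion, so a mild case could be reduced under either reading.
- *That akathisia is caught in the same contradiction.* Section 5.1.1.2 has parallel wording for it ("treatment with AUSTEDO, the AUSTEDO dose will be reduced; some subjects may require"), but 2.3 and 3.6.1.8 never mention akathisia. What remains is a specific instruction beside the general discretion in 3.5.1.2 and item d. That is at most a tension.
- *That the primary proportion could shift by as much as 20 points.* This needs three affected subjects (3/15), all otherwise successes, and no figure in the documents supports that count. The tardive dyskinesia trial of 117 subjects described in section 1.2.2 saw no worsening of parkinsonism on the UPDRS motor subscale. That is a different population and gives no rate of mild cases, but it does not point to a large number.

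It is also fair to say that much of the needed information is already collected. Reasons for not reaching or keeping the dose (3.7.1.1), reductions due to adverse events (3.1) and the severity grade of each event (5.1.2.1) are all recorded. Severity is not the same as clinical significance, but it comes close.

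**Conclusion.** The inconsistency is real for parkinsonism and only for parkinsonism. A subject with parkinsonism judged not clinically significant is a certain failure under 5.1.1.2 and a possible success under 2.3 and 3.6.1.8. The success depends on the investigator leaving the dose unchanged and on the subject otherwise completing at target.

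Each such subject is worth 6.7 points on a denominator of 15. That is small beside the exact interval, which is 95.7 − 51.9 = 43.8 points wide at 12/15. But it comes from an ambiguous rule, not from sampling. The number of affected subjects is unknown, and the chances in Step 4 rest entirely on assumed rates.

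This is a modest point that should be fixed because the ambiguity feeds the primary endpoint and costs almost nothing to remove. Which rule is clinically right is not judged here.

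**What to change.** 1. Reconcile 5.1.1.2 with 2.3, 3.6.1.8 and the dose-limiting toxicity definition, so that one rule, chosen by the clinical team, states when parkinsonism leads to a dose change. Alternatively, state that the 5.1.1.2 list is label background and name the section that governs. While editing, say how the akathisia entry in 5.1.1.2 relates to the general discretion in 3.5.1.2.
2. For every reduction attributed to parkinsonism, record whether the sign was judged clinically significant at the time, next to the reason and severity already collected.
3. Report the primary proportion as defined, and again with subjects reduced only for non-significant parkinsonism counted as successes. Label the second figure an upper bound, since it assumes that they would have reached and completed at the target dose.

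The cost is a wording change in the affected sections, one extra field on the dose-change or adverse event record, and one extra line in the results table. No added visits, assessments or subjects are needed.

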5.1.2.1 Assessment of Severity

The severity of each AE/SAE will be classified into one of three defined categories as follows:

- Mild: the AE is easily tolerated by the subject, causes minimal discomfort, and does not interfere in a significant manner with the subject's normal functioning level or activities
- Moderate: the AE is sufficiently uncomfortable to interfere with normal everyday activities, but is not hazardous to health
- Severe: the AE produces significant impairment of functioning or incapacitation and is a definite hazard to the subject's health.

These three categories are based on the investigator's clinical judgment, which in turn depends on consideration of various factors such as the subject's reports, the physician's observations, and the physician's prior experience.

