3.6.1.2 ECG

AUSTEDO may prolong the QT interval. QT interval prolongation is associated with the development of tachyarrhythmias and Torsades de Pointes. To screen for the development of significant QT

prolongation (defined as a corrected QT –Bazett– interval of 450 (458) milliseconds in men or 460 (472) milliseconds in women), a 12-lead electrocardiogram (ECG) will be performed during all scheduled study Visits, including the early termination Visit, if such a Visit happens. Should there be evidence of QT prolongation, it will remain at the investigator's discretion to either discontinue the study drug, or to reduce the dose to a new, maximum, well-tolerated dose. A follow up ECG will be performed 1 week after the dose reduction (during an unscheduled Visit) to ensure the QT prolongation is no longer significant.

However, a study subject will be asked to discontinue study drug if at any point during the trial he or she is found on ECG to have developed a QTc> 500 milliseconds or a QTc increase of >60 milliseconds from baseline. Study subjects will be asked to come in for an Early Termination Visit within 3 business days of study drug discontinuation.

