4.10 Treatment Compliance

During Visit 1, the total number of tablets that each study subject will need for the duration of the trial will be dispensed. Compliance will be assessed during Visit 5, that is, during the 1-week post-treatment Visit. The number of returned tablets will be counted by the Investigator, or a designee, and recorded in the Drug Dispensing Log. At least 80% compliance will be defined as acceptable in this study. Compliance with study drug intake will be assessed verbally (subject's report, no tablet counting) and encouraged during all other study Visits.

- 5. ADVERSE EVENTS
- 5.1 Definitions
- 5.1.1 Adverse Event Definitions

During the study, the Investigator or study site personnel will be responsible for querying and recording adverse events (AEs) and serious adverse events (SAEs), as detailed in this section of the protocol. This includes the weekly communications with the study subjects via telephone during the ramp-up period. In this study AEs and SAEs will be reported from the time of study drug administration until the last study Visit or death, whichever occurs first.

An adverse event (AE) is any untoward medical occurrence that occurs in conjunction with the use of a medicinal product in humans, whether or not considered to have a causal relationship to the medicinal product. An AE can, therefore, be any unfavorable or unintended sign (including a clinically significant abnormal laboratory finding), symptom, or disease temporally associated with the use of a medicinal product, whether or not it is a direct consequence of study drug use.

Any medical condition or clinically significant laboratory abnormality with an onset date before the first date of study drug administration will be considered to be pre-existing, and will not be recorded as an AE. Any AE (i.e., a new event or an exacerbation of a pre-existing condition) with an onset date after study drug administration up to and including the designated follow-up safety Visit will be recorded as an AE. All AEs will be recorded regardless of the severity or relationship to study medication. All AEs that result in permanent discontinuation of the study drug being studied, whether serious or nonserious, will be reported.

An AE does include:

- an exacerbation of a pre-existing illness
- an increase in frequency or intensity of a pre-existing episodic event or condition

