5.6 Stopping Rule

A study subject will be asked to discontinue study drug if at any point during the trial he or she is found on ECG to have developed a QTc> 500 milliseconds or a QTc increase of >60 milliseconds from baseline. Study subjects will be asked to come in for an Early Termination Visit within 3 business days of study drug discontinuation.

- 6. DATA ANALYSIS / STATISTICAL METHODS
- 6.1 Data Summary
- 6.1.1 Summary of Safety Data

The safety analysis population will include all enrolled subjects who receive at least one dose of study drug. Demographic data and key baseline characteristics will be summarized for the Safety population. Safety data will be summarized from the time of first dose and include all available safety data.

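### The three AE severity definitions in 5.1.2.1 mix functional effect with hazard, so some events have no grade and others can only be graded lower than their effect or hazard suggests

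*Combined protocol and SAP*

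**What the plan says.** Section 5.1.2.1 places every AE and SAE in one of three defined categories:

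- "Mild: the AE is easily tolerated by the subject, causes minimal discomfort, and does not interfere in a significant manner with the subject's normal functioning" (the sentence goes on to activities and contains no hazard condition).
- "Moderate: the AE is sufficiently uncomfortable to interfere with normal everyday activities, but is not hazardous to health" (here any hazard rules the grade out).
- For the top grade, two conditions are joined: "Severe: the AE produces significant impairment of functioning or incapacitation and is a definite hazard to the subject's health".

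It then adds: "These three categories are based on the investigator's clinical judgment, which in turn depends on consideration of various factors".

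The AE form (Figure 1 in 3.6.1.1) offers only these three boxes. Sections 5.1.1 and 5.3 make severity, called intensity in 5.3, a recorded attribute of every AE.

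Two foreseeable events matter here. Section 5.6 takes a subject off study drug if he or she is "found on ECG to have developed a QTc> 500 milliseconds or a QTc increase of >60 milliseconds from baseline", and 3.6.1.2 explains that "QT interval prolongation is associated with the development of tachyarrhythmias and Torsades de Pointes". Section 5.1.1.2 states that "Sedation is a common dose-limiting adverse reaction of AUSTEDO".

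**The concern.** A severity scale should give every event exactly one grade, and the grade should rise as the event gets worse. This scale runs on two dimensions, effect on functioning and hazard to health, but handles hazard differently at each step: ignored in Mild, excluded in Moderate, required in Severe. Events that score high on one dimension and low on the other may be graded low or have no box. Two careful investigators could then grade the same event differently, each defensibly.

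Safety and tolerability are the primary objective (2.1), there is no control arm, and 15 subjects are planned (3.3). The AE description is therefore a substantial part of what the trial will report, and severity is one of the attributes collected for it.

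**Working it through.** The plan states no figure on this point, so there is none to reproduce. The check applies the three definitions literally to every combination of the two attributes they use.

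**Inputs, all from 5.1.2.1**

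- Functional effect, three levels: minimal; interferes with everyday activities; significantly impairing or incapacitating.
- Hazard to health, two levels: no; yes (definite).
- Mild = minimal effect, whatever the hazard.
- Moderate = at least interference, and no hazard.
- Severe = significant impairment or incapacitation, and a definite hazard.

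**Result: 3 × 2 = 6 combinations**

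| Functional effect | Hazard | Grade under the present text | Grade if Severe uses *or* and Mild excludes hazard |
|---|---|---|---|
| Minimal | No | Mild | Mild |
| Minimal | Yes | Mild only | Severe |
| Interferes | No | Moderate | Moderate |
| Interferes | Yes | None fits | Severe |
| Impairing or incapacitating | No | Moderate at most | Severe |
| Impairing or incapacitating | Yes | Severe | Severe |

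Three of the six rows are graded consistently now: minimal without hazard, interfering without hazard, and impairing with hazard. In the last column each row has one grade. The fifth row meets both the Moderate and the Severe wording under *or*, so a highest-grade rule is needed to settle it.

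**Examples**

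- *Minimal effect, hazard.* An asymptomatic QTc above 500 ms is an unintended sign and so can be an AE under 5.1.1. It causes no discomfort and no loss of function, so neither Moderate nor Severe fits. Yet 5.6 requires study drug to stop for it, and 3.6.1.2 gives arrhythmia as the reason for screening.
- *Interference, hazard.* Take an event that disturbs daily activities and puts the subject at risk, where the investigator finds the impairment short of significant. Its hazard bars it from Moderate, its lesser impairment bars it from Severe, and its interference bars it from Mild.
- *Impairment or incapacity, no definite hazard.* Sedation that keeps a subject from normal functioning, but is not judged a definite hazard, cannot be Severe.

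**A further gap from the two hazard terms.** The table treats hazard as yes or no. The text asks for a definite hazard in Severe but excludes anything hazardous from Moderate. An incapacitating event with some hazard, short of definite, is therefore shut out of both.

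**Where the grade is used.** Dose-limiting toxicity (3.5.2.4), the QTc stopping rule (5.6), suicidality (2.3) and SAE reporting (5.4) have their own criteria, and none refers to the severity grade. The primary safety endpoint (3.7.1.1) is the proportion of subjects who reach the maximal dose and complete the study on it. Section 6.1.1 summarises all available safety data but specifies no table by severity.

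**The case against.** The strongest reply is that grading rests on clinical judgment, that nothing depends on the grade, and that the dangerous events are captured elsewhere. Much of this stands. Section 5.1.1 says "All AEs will be recorded regardless of the severity or relationship to study medication", and AEs that end study drug permanently are reported whether serious or not. QTc and suicidality have scheduled assessments and their own discontinuation rules. An important medical event can be classed as serious under 5.1.1.2 whatever its severity. A stop for QTc would therefore not disappear from the record, even if a severity summary showed no severe AE.

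The appeal to judgment does not close the gap. Judgment decides whether there is impairment and whether there is hazard. It supplies no category for interference with hazard and adds no hazard condition to Mild.

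A reader might infer more than the text supports:

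- *Incapacitating sedation can never be Severe.* It can, whenever the investigator judges it a definite hazard. Incapacity is not required either, because significant impairment also meets the first part.
- *Suicidal ideation with unchanged function grades as Mild.* Mild also requires that the event be easily tolerated with minimal discomfort, which cannot be assumed for ideation.
- *Each misgraded subject shifts a key result by 1/15 = 6.7 percentage points.* The arithmetic is right, but the proportion of subjects with any severe AE is not a planned measure.
- *The trial's severity results would mislead beside the open-label tic study in 1.2.2, summarised there as having no serious or severe events.* That study's severity definition is not in the documents, so the comparison shows nothing about this scale.

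**Conclusion.** The concern holds as a defect of definition. The scale is not exhaustive and can under-grade: of six combinations, one has no grade, one is barred from Severe despite significant impairment or incapacity, and one fits only Mild despite a hazard. The count of three in six describes the wording and gives equal weight to each combination. The documents offer no basis for forecasting how many events would be affected.

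The conclusion rests on reading the definitions literally, on an asymptomatic QTc above 500 ms being recorded as an AE and regarded as a hazard, and on impairment and hazard being judged separately. Treating a hazardous event as more than Mild is an inference, but it follows the scale's own logic, since Moderate already excludes hazard.

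The effect is confined to the description of AE severity. It does not touch subject protection, the primary endpoint or SAE reporting. The change is still worth making, because safety is the primary objective, severity is recorded for every AE, and the correction is nearly free.

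**What to change.** In 5.1.2.1:

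1. In Severe, replace the *and* that joins functional impairment to hazard with *or*.
2. Add to Mild the same exclusion of hazard that Moderate already has.
3. Use one hazard term in all three definitions, so that Mild and Moderate exclude exactly what Severe includes.
4. State that the highest applicable grade is recorded, and repeat this as a note on the AE form (Figure 1).

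In 6.1.1, add that AEs leading to discontinuation of study drug are listed separately from any summary by severity. A statement about severe AEs will then always stand beside the events that ended treatment.

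A rule that every event meeting a discontinuation criterion is automatically severe is not needed. It would turn an intensity scale into a second seriousness flag. For example, a passing positive answer to the first C-SSRS ideation item could then be tabulated as a severe AE.

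The cost is a few words in 5.1.2.1, a note on the form and one sentence in 6.1.1. The downside is that somewhat more events will be labelled severe.
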